### **Randomization and Allocation**

Eligible patients were randomized in a 1:1 ratio to either the intervention group (HPTC peritoneal reconstruction) or the control group (standard peritonectomy closure). Randomization was performed using a computer-generated block randomization sequence with variable block sizes to ensure balanced group allocation across participating centers.

Allocation concealment was achieved using sealed, opaque envelopes opened intraoperatively after completion of cytoreduction and confirmation of peritoneal defect suitability. Due to the nature of the surgical intervention, blinding of the operating surgeon was not feasible. However, outcome assessors, radiologists evaluating imaging studies, and statisticians were blinded to treatment allocation wherever applicable.

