### **Postoperative Care and Follow-Up**

Postoperative management protocols, including analgesia, antibiotic prophylaxis, early mobilization, and nutritional advancement, were standardized across centers. Nasogastric decompression was discontinued at the discretion of the treating team based on bowel function recovery.

Patients were followed for a minimum of two months postoperatively, with scheduled clinical assessments at discharge, 30 days, and 60 days. Imaging studies and quality-of-life assessments were performed according to protocol-defined timelines.

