### **Outcome Measures**

#### **Primary Outcome**

The primary outcome was the incidence of major intra-abdominal complications within two months following surgery. Major complications were predefined as:

- Adhesive small bowel obstruction requiring intervention
- Enterocutaneous fistula
- Reoperation for intra-abdominal complication
- Grade  $\geq 3$  wound complications based on the Clavien–Dindo classification

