#### **Secondary Outcomes**

Secondary outcomes included:

- Individual complication rates, including intraperitoneal adhesions, bowel obstruction, surgical site infection, incisional hernia, and fistula formation

- Time to bowel function recovery, defined as the time to first flatus and tolerance of oral diet
- Length of intensive care unit (ICU) stay and total hospital stay
- Device-related adverse events, including infection, inflammatory reaction, or mesh-related complications
- Radiologic assessment of adhesions or obstruction using magnetic resonance imaging (MRI) at baseline, one month, and two months
- Quality of life assessment using the European Organisation for Research and Treatment of Cancer Quality of Life Questionnaire Core 30 (EORTC QLQ-C30), a validated cancer-specific instrument [20]

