### Statistical Analysis Plan

Statistical analyses were performed using SPSS version 29.0 (IBM Corp., Armonk, NY, USA). Continuous variables were assessed for normality using the Shapiro–Wilk test and are presented as mean  $\pm$  standard deviation for normally distributed data or median with interquartile range for non-normally distributed data. Between-group comparisons were conducted using the independent t-test or Mann–Whitney U test for continuous variables and the chi-square test or Fisher’s exact test for categorical variables, as appropriate. Effect estimates for the primary and key secondary binary outcomes were expressed as relative risks with 95% confidence intervals. Time-to-event outcomes, including time to bowel function recovery, were analyzed using Kaplan–Meier survival curves with log-rank testing. Multivariable logistic regression analysis was performed to adjust for potential confounders, including age, primary tumor type, peritoneal cancer index score, and use of hyperthermic intraperitoneal chemotherapy. All statistical tests were two-sided, and a p-value  $< 0.05$  was considered statistically significant. Analyses were conducted on an intention-to-treat basis.

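### The plan has no rule for death before bowel recovery or discharge, so an in-hospital death would by default be scored as a short, favourable stay

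*Combined protocol and SAP*

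**What the plan says.** Secondary Outcomes lists two outcomes that death can cut short: "Time to bowel function recovery, defined as the time to first flatus and tolerance of oral diet", and "Length of intensive care unit (ICU) stay and total hospital stay".

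The Statistical Analysis Plan assigns the first to survival methods: "Time-to-event outcomes, including time to bowel function recovery, were analyzed using Kaplan–Meier survival curves with log-rank testing". It does not name stay. The rule that stay most naturally falls under is "Between-group comparisons were conducted using the independent t-test or Mann–Whitney U test for continuous variables". The analysis set is also fixed there: "Analyses were conducted on an intention-to-treat basis". Postoperative Care and Follow-Up adds "Patients were followed for a minimum of two months postoperatively", with assessments at discharge, 30 days and 60 days.

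The plan contains no censoring rule, no competing-event method, no value for a patient who dies in hospital and no mortality endpoint. The four components under Primary Outcome are adhesive obstruction requiring intervention, fistula, reoperation and grade 3 or higher wound complications. Death is not among them.

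**The concern.** Recovery of bowel function and discharge home are good outcomes, and death prevents both. Intention-to-treat keeps the patient who died in the analysis, so that patient needs a value, and the plan supplies none. What then happens depends on the default behaviour of the methods.

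- **Stay.** A patient who dies in hospital on day 4 contributes 4 days, which ranks among the best results in the arm.
- **Bowel recovery.** A death is usually censored. Kaplan–Meier then treats the patient as someone who could still recover later, and the curve rises above the proportion who actually recovered.

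Because death appears neither in the primary composite nor as an outcome of its own, no other listed result would offset the error. With 30 patients per arm, a few deaths can matter.

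**Working it through.** **Inputs from the documents.** 30 patients per arm, 1:1 allocation, two-sided 0.05 (so 2.5% in each direction), and the tests named above. The plan gives no design figure for stay, recovery or mortality, so there is none to reproduce. Its sample-size calculation concerns the primary outcome and does not enter here.

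**Assumptions not in the documents.** The number and timing of deaths, and the distributions of stay and recovery, as stated at each step.

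**1. Fixed example.** Take two identical arms of 30, with lognormal quantiles and log-SD 0.5. Median recovery is 5 days and median stay 14 days. In one arm the *k* slowest patients die on day 2.

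*Recovery by day 7.* In each arm 22 of 30 recover by day 7, one of them before day 2. The slowest patients would have recovered after day 7, so the deaths do not change the 22.
- Cumulative incidence: 22/30 = 73.3% in both arms.
- Kaplan–Meier with deaths censored: 1 − (29/30) × [1 − 21/(29 − *k*)].
- *k* = 1: 1 − (29/30)(7/28) = 75.8%.
- *k* = 3: 1 − (29/30)(5/26) = 81.4%.

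The log-rank Z is +0.45 for *k* = 1 and +1.12 for *k* = 3. Both favour the arm with the deaths, and neither is significant.

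*Mean stay.* The longest stay is 14 × exp(0.5 × 2.128) = 40.6 days. Replacing it with 2 days lowers the mean by (40.6 − 2)/30 = 1.3 days, from 15.8 to 14.5. With *k* = 3 the mean is 12.6 days and the Mann–Whitney p-value is 0.21. If deaths are ranked worst, p is 0.95.

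**2. Stay when the arms do not truly differ.** Lognormal stay, median 13 days, log-SD 0.45, deaths on days 2–6 in one arm, Mann–Whitney on raw days. Ranges are across repeated runs.

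| Early deaths in one arm | That arm falsely declared better |
|---|---|
| 0 | 2.3% |
| 1 | 3.6–4.2% |
| 2 | 5.3–5.5% |
| 3 | 7.7–8.0% |

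**3. Stay when the arms truly differ.** Medians of about 13.5 and 10 days, other settings as in step 2. Power with no deaths is about 69%.
- Deaths in the shorter-stay arm: 1, 2 or 3 deaths raise apparent power to about 75%, 80% and 84–86%.
- Deaths in the longer-stay arm: power falls to about 58%, 45% and 32%.

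**4. Does it matter who dies?** No true effect on recovery or stay; medians and log-SD as in step 1; deaths spread over days 1–14; 2,000 trials. The simulation standard error near 2.5% is √(0.025 × 0.975/2000), or about 0.35 points. The table shows how often the arm with deaths is falsely favoured.

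| Mortality, one arm vs other | Who dies | Raw stay, Mann–Whitney | Log-rank, deaths censored |
|---|---|---|---|
| 5% vs 0% | unrelated to recovery | 3.8% | 2.6% |
| 5% vs 0% | sicker patients | 7.1% | 3.9% |
| 10% vs 0% | unrelated to recovery | 6.5% | 2.9% |
| 10% vs 0% | sicker patients | 14.1% | 5.0% |

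With 5% mortality in both arms, neither test shows a systematic lean. In a separate simulation with a true difference in recovery, log-rank power was 62% with no deaths and 60%, 57% and 58% with 1, 2 and 3 deaths censored. The simulation error there is about 1.3 points.

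**The case against.** **The plan is silent; it does not prescribe a wrong rule.** A reader might infer that the plan directs deaths to be censored or counted as completed stays. It does neither. It also never assigns stay to a t-test or rank test, and its wording on time-to-event outcomes is open enough to include stay. This stands: the defect is a missing rule, and the harm comes from the most natural default.

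**The log-rank test is barely affected.** A reader might infer that censoring deaths biases the bowel-recovery test toward the arm with deaths. The calculations do not support that in general. When death is unrelated to recovery the test is about neutral, and a lean appears only if slow recoverers are the ones who die. For this outcome the concern is confined to the Kaplan–Meier proportions, plus that conditional case.

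**The direction need not favour the device.** If the mesh shortens stay and the deaths fall in the control arm, raw scoring works against the mesh (step 3). The error favours whichever arm has more early deaths, and the documents do not say which arm that would be.

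**Early deaths may be few.** Eligibility requires ECOG 0–2 and adequate organ function, and excludes emergency surgery. This lowers the risk without removing it. In the fixed example no comparison reached significance, even with three deaths.

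**The remedies answer different questions.** Ranking deaths worst brings mortality into the comparison of stay. This is a fair point about cost, but it does not justify leaving the rule unstated.

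**Conclusion.** The point holds as a missing rule for death, and it affects secondary outcomes only.

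For stay, analysing raw days by intention to treat scores an in-hospital death as a favourable result, whether or not death is related to recovery. With no true difference and an assumed 1 to 3 early deaths in one arm, the false-favourable rate for that arm rises from a nominal 2.5% to about 4–8%. For bowel recovery, the Kaplan–Meier curve overstates the proportion recovered, by 2.5 points at day 7 with one death in the fixed example (75.8 − 73.3), while the log-rank test is about neutral except in the case described above.

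All sizes rest on assumed distributions and on the number and imbalance of deaths, which the documents do not give. If no one died before recovery or discharge, nothing changes. If mortality was equal in the two arms, the between-arm comparisons are not shifted on average.

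**What to change.** Add these rules to the Statistical Analysis Plan:

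- **ICU and hospital stay:** compare by Mann–Whitney with in-hospital deaths ranked as the worst value. Show stay among patients discharged alive as a descriptive addition.
- **Bowel recovery:** present cumulative incidence with death as a competing event in place of Kaplan–Meier. With complete follow-up this is the number recovered by each day divided by the number randomised to the arm.
- **Both:** report deaths by arm beside these results.

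Keeping deaths in the log-rank risk set to day 60 is a possible alternative for recovery, but it gives each death heavy leverage. In simulation, one death in the faster-recovering arm cut power from about 59% to 25%. Cumulative incidence corrects the displayed proportions without making the log-rank test carry that weight.

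**Cost.** A few sentences, and dates of death, recovery and discharge, which follow-up to day 60 should already provide. No extra patients or visits are needed. The real downside is interpretive: worst-rank stay combines mortality with stay. At 30 per arm each death carries noticeable weight, now against the arm in which it occurs, so the result must be read with the deaths by arm.

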### **Study Population**

Patients were consecutively screened for eligibility during multidisciplinary tumor board evaluation at participating centers. Adults aged 18–75 years with histologically confirmed peritoneal surface malignancy (including colorectal, ovarian, appendiceal, pseudomyxoma peritonei, or malignant peritoneal mesothelioma) scheduled to undergo cytoreductive surgery with anticipated peritonectomy, with or without hyperthermic intraperitoneal chemotherapy, were considered eligible. Additional inclusion criteria included Eastern Cooperative Oncology Group (ECOG) performance status 0–2 [19], adequate hematologic, renal, and hepatic function, and ability to provide written informed consent.

Exclusion criteria comprised known hypersensitivity to collagen-based products, active intra-abdominal infection or uncontrolled sepsis, chronic immunosuppression or long-term systemic corticosteroid therapy, pregnancy or lactation, extensive small-bowel resection precluding safe reconstruction, and emergency surgery or bowel perforation at presentation.

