### Sample Size Calculation

Based on prior literature reporting postoperative complication rates of approximately 40–45% following extensive peritonectomy, a reduction to 15–20% in the intervention group was considered clinically meaningful. The required sample size for comparing two independent proportions was estimated using the formula:

$$n = ((Z_{1-\alpha/2} + Z_{1-\beta})^2 \times [p_1(1-p_1) + p_2(1-p_2)]) / (p_1 - p_2)^2$$

where  $p_1$  represents the expected complication rate in the control group and  $p_2$  the expected rate in the intervention group,  $Z_{1-\alpha/2}$  corresponds to the two-sided significance level  $\alpha=0.05$ , and  $Z_{1-\beta}$  to the desired power (80%). Assuming  $p_1=0.40$  and  $p_2=0.20$ , the calculated minimum sample size was 26 patients per group. To account for potential dropouts and protocol deviations, 30 patients were enrolled in each arm, yielding a total sample size of 60 participants.

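### The adjusted logistic model may have only about two expected events per coefficient, so ordinary maximum likelihood would tend to exaggerate any real treatment effect

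*Combined protocol and SAP*

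**What the plan says.** The Statistical Analysis Plan section compares categorical outcomes by chi-square or Fisher's exact test and says: "Effect estimates for the primary and key secondary binary outcomes were expressed as relative risks with 95% confidence intervals". It then adds a model: "Multivariable logistic regression analysis was performed to adjust for potential confounders, including age, primary tumor type, peritoneal cancer index score", with HIPEC use as the last listed covariate.

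The section does not say which outcome the model addresses, how tumour type is coded, or what happens if a category is sparse or the fit does not converge. Nor does it say whether the model is primary or supportive. One rule covers every test: "All statistical tests were two-sided, and a p-value" below 0.05 counts as significant.

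The Study Population section lists five eligible tumour types: "including colorectal, ovarian, appendiceal, pseudomyxoma peritonei, or malignant peritoneal mesothelioma". The Sample Size Calculation section assumes 0.40 in the control arm and 0.20 in the intervention arm, with 30 patients enrolled per arm. Its background ranges are "postoperative complication rates of approximately 40–45" per cent for control, and "a reduction to 15–20% in the intervention group was considered clinically meaningful".

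**The concern.** The number of events, not the number of patients, limits what a logistic model can support. Sixty patients at the design rates give few events. A five-level tumour factor with age, PCI, HIPEC and treatment uses up most of that information.

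Two problems follow when such a model is fitted by maximum likelihood. A real effect is pushed away from the null by small-sample bias, so the adjusted odds ratio flatters the device. Also, a tumour type in which no patient, or every patient, has an event has no finite coefficient, and the plan gives the analyst no rule for that case.

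The model also yields an odds ratio, whereas the stated effect measure is the relative risk. The adjusted result would therefore be on a different scale from the main one.

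**Working it through.** **1. The plan's own figure.** The plan gives no figure for the adjusted model. Its only calculation is the sample size. The stated formula with the stated inputs gives (1.960 + 0.842)² × (0.24 + 0.16) / 0.20² = 7.849 × 0.40 / 0.04 = 78.5, so 79 per group, not the stated 26. That is a separate matter. Here it explains why events are few. The steps below use the 30 per arm that were enrolled.

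**2. Expected events** (all 60 patients contributing).
- Design rates: 30 × 0.40 + 30 × 0.20 = 12 + 6 = 18.
- Stated ranges: from 30 × (0.40 + 0.15) = 16.5 to 30 × (0.45 + 0.20) = 19.5.
- Sampling variation around 18: about 11 to 25.

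**3. Events per coefficient** (intercept not counted). The coding of tumour type is an assumption, because the plan does not state it.

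| Tumour type entered as | Coefficients | Events per coefficient |
|---|---|---|
| Five separate types (4 indicators) | 1 + 1 + 4 + 1 + 1 = 8 | 18/8 = 2.25 (16.5/8 = 2.06 to 19.5/8 = 2.44) |
| One binary term | 5 | 18/5 = 3.6 |
| Left out | 4 | 18/4 = 4.5 |

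**4. Simulation of the 8-coefficient model.** There were 60 patients and 2,000–3,000 replicates per scenario. The documents give no tumour mix, so three were assumed: equal; moderate (30/30/15/15/10%); skewed (35/35/15/10/5%). Covariates were either unrelated to outcome or moderately prognostic. In the prognostic rows the true value is the conditional log odds ratio, so the ordinary difference between conditional and marginal odds ratios is not counted as bias. Maximum-likelihood means leave out the few data sets in which the treatment estimate diverged.

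| Mix, covariates, rates | True log OR | ML mean (excess) | Firth mean | Some coefficient not finite |
|---|---|---|---|---|
| Equal, unrelated, 0.40/0.20 | −0.981 | −1.186 (21%) | −0.972 | 11.5% |
| Equal, prognostic, 0.40/0.20 | −1.084 | −1.381 (27%) | −1.103 | 13.9% |
| Moderate, prognostic, 0.40/0.20 | −1.083 | −1.378 (27%) | −1.108 | 31.7% |
| Skewed, unrelated, 0.40/0.20 | −0.981 | −1.210 (23%) | −0.999 | 54.4% |
| Skewed, prognostic, 0.40/0.20 | −1.083 | −1.314 (21%) | −1.066 | 60.0% |
| Equal, prognostic, 0.45/0.15 | −1.691 | −2.170 (28%) | −1.731 | 13.2% |

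The excess is the ML mean divided by the true value, minus 1; for example 1.186/0.981 − 1 = 21%.

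- *Medians.* With unrelated covariates at 0.40/0.20 the median log ORs are −1.134 and −1.172, which are ORs of 0.32 and 0.31 against a true 0.375. On the log scale 1.134/0.981 − 1 = 16%. A further run with about 16 events gave a median near 0.30, and Firth's fit of the same model gave about 0.38.
- *Unadjusted odds ratio.* It is itself 4–7% too far from zero on the log scale in the unrelated-covariate scenarios at 0.40/0.20 and 0.45/0.15, so not all of the excess comes from the covariates.
- *No true effect (0.30 in both arms).* The ML mean log OR is −0.01 to 0.02. Type I error of the adjusted test is 5–6%.
- *Coverage.* The 95% interval for treatment covers in about 94–96% of data sets across scenarios.
- *Treatment coefficient.* It diverged in at most 1.6% of data sets. The non-finite terms are tumour-type coefficients.

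**5. Scale.** At the design rates the relative risk is 0.20/0.40 = 0.50, and the odds ratio is (0.20/0.80)/(0.40/0.60) = 0.375.

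**The case against.** The plan ties the primary outcome to relative risks and to chi-square or Fisher tests. The natural reading is that the regression is supportive. This largely stands: the plan does not say so, but nothing makes the model primary either. The point therefore concerns a secondary estimate, not the main result.

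The count of 8 is conditional. Merged tumour types would give 5 to 7 coefficients. This stands, but even one binary term leaves 3.6 events per coefficient, and the covariate list is worded so that it need not be complete.

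The bias is small beside the imprecision. In the first row of the table it is 1.186 − 0.981 = 0.205 on the log scale, against a median standard error of about 0.70. This also stands, and it is why coverage holds up. It does not excuse a systematic shift that a simple change of fitting method nearly removes.

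The low event count is mostly a result of the sample size. At 79 per arm one would expect 79 × 0.60 = 47 events, or 5.9 per coefficient. That is true, but the model has to suit the 60 patients enrolled.

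A reader might infer more than this:
- *That the treatment effect cannot be estimated.* It was finite in at least 98% of simulated data sets.
- *That the model creates a benefit where none exists.* With equal rates there was no material bias, and type I error was near nominal.
- *That the primary outcome is tested twice at 0.05.* The plan does not name the model's outcome. If both tests did address it and either could be claimed, simulated false-positive rates were about 7–9%. A label would settle this.
- *That an odds ratio will be headlined.* No section says so.

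**Conclusion.** The concern holds in limited form. If the model is applied to the primary outcome with five separate tumour types, there are about 2.25 expected events per coefficient. If a true effect exists, maximum likelihood will tend to overstate it by roughly 16–28% on the log odds ratio scale. One or more tumour-type coefficients will be non-estimable in about 10–60% of data sets.

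The event count rests on the design rates and 30 evaluable patients per arm. The coefficient count rests on unmerged tumour types. The non-estimability range rests on assumed tumour mixes, and the size of the bias on the assumed rates and covariate effects. The unlabelled primary analysis and the odds-ratio scale are gaps in labelling, not demonstrated errors.

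**What to change.** Fit the adjusted model with Firth penalised likelihood, and state its outcome and the coding of tumour type. Prespecify that sparse types are merged if needed. In the simulations the penalty alone brought the mean log odds ratio to within about 2.5% of the true value with all 8 coefficients kept.

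Label this model a sensitivity analysis to the randomised relative-risk comparison. Report from it a standardised relative risk and risk difference: predict each patient's risk under both arms, average within arm, and take the ratio and the difference. The penalty pulls predicted risks towards one half, so re-estimate the intercept before averaging.

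A smaller covariate set is a matter of choice. In one simulation a model with treatment, PCI and HIPEC gave a median odds ratio of 0.36–0.37 against 0.375.

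The cost is a few sentences in the SAP, a penalised routine that may lie outside base SPSS, and coarser adjustment for tumour type if types are merged. The document is written in the past tense. If the data have already been analysed, the refit should still be reported but identified as post hoc.

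### The plan does not name the decisive analysis of the primary outcome; if the unadjusted or the adjusted result may be claimed, the type I error can rise from 5% to roughly 6–8.5%

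*Combined protocol and SAP*

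**What the plan says.** The Primary Outcome section defines one binary composite, assessed over two months. The Statistical Analysis Plan section then contains four statements that bear on it:

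- Chi-square or Fisher's exact test is used "for categorical variables, as appropriate". No rule for choosing between them is given.
- Primary and key secondary binary outcomes are summarised as relative risks with 95% confidence intervals.
- "Multivariable logistic regression analysis was performed to adjust for potential confounders"; age, tumour type, peritoneal cancer index and HIPEC are named as examples. The model's outcome is not stated, nor whether it is primary or supportive, and the covariate list is open-ended.
- "All statistical tests were two-sided", and a p-value below 0.05 "was considered statistically significant".

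No sentence there, or in the Primary Outcome or Sample Size Calculation sections, says which analysis decides the trial.

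**The concern.** A 5% error rate belongs to one pre-specified test. When two analyses of the same endpoint can each produce a p-value below 0.05, and nothing says which one counts, the level holds only if the choice does not depend on the results. The plan does not secure that. The trial is open-label, and the Randomization and Allocation section blinds statisticians only where this applies.

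The adjusted model is the weaker candidate for a decisive role. It fits many terms to few events, and the plan does not say whether its p-value comes from a Wald or a likelihood-ratio test.

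**Working it through.** **Inputs from the documents.** "Eligible patients were randomized in a 1:1 ratio"; 30 per arm, 60 in total; two-sided alpha 0.05; planned rates 0.40 (control) and 0.20 (intervention), within the literature range of "postoperative complication rates of approximately 40–45% following extensive peritonectomy" and the target "a reduction to 15–20% in the intervention group was considered clinically meaningful".

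**Inputs assumed.** A common null event rate of 0.15–0.45; five tumour types; HIPEC in half the patients; covariate effects set to none, moderate (log-odds 0.4 per SD for age, 0.8 per SD for cancer index, 0.6 for HIPEC, −0.3 to 0.5 between tumour types) or strong (twice these). The covariate set was held fixed.

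**Step 1: the plan's own figures.** The plan's formula gives (1.960 + 0.842)² × (0.24 + 0.16) / 0.20² = 7.849 × 0.40 / 0.04 = 78.5, so 79 per group, not the stated 26. That is a separate point. Everything below uses the 30 per arm actually planned.

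**Step 2: chi-square against Fisher.** All 30 vs 30 tables were enumerated exactly. None has Fisher p<0.05 with uncorrected chi-square p≥0.05, so a free choice between the two has the size of chi-square alone.

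| Common rate | Chi-square | Fisher | Fisher if any expected count <5, else chi-square |
|---|---|---|---|
| 0.20 | 4.9% | 2.2% | 4.2% |
| 0.30 | 4.9% | 2.6% | 4.9% |
| 0.40 | 4.9% | 2.6% | 4.9% |
| 0.45 | 5.1% | 2.7% | 5.1% |

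**Step 3: power under that expected-count rule.** At 40% vs 20% it is 39.2%, against 39.3% for chi-square throughout; the rule selects Fisher in 0.5% of trials. At 45% vs 15% both give 73.7%. At 20% vs 10%, well below the plan's rates, power is 13.3% against 19.4%.

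**Step 4: adding the adjusted model.** Null trials were simulated (6,000 per setting, Monte Carlo standard error about 0.3 points). The table shows how often at least one p-value fell below 0.05, for covariate effects none / moderate / strong.

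| Common rate | Expected-count rule or Wald | Any of chi-square, Fisher, Wald |
|---|---|---|
| 0.20 | 6.1 / 6.7 / 6.9% | 6.6 / 7.1 / 7.5% |
| 0.30 | 7.1 / 7.6 / 8.2% | 7.1 / 7.7 / 8.2% |
| 0.40 | 7.2 / 7.3 / 7.7% | 7.2 / 7.3 / 7.7% |
| 0.45 | 7.0 / 8.1 / 8.5% | 7.0 / 8.1 / 8.5% |

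At a rate of 0.15 the ranges are 4.6–5.1% (rule or Wald) and 6.7–6.9% (any of three). Two further simulations with their own assumed covariates gave 6.3–7.9% (rule or Wald) and 7.4% (any of three).

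**Step 5: stability of the logistic model.** With five tumour types there are 1 (treatment) + 1 (age) + 1 (cancer index) + 1 (HIPEC) + 4 (tumour type) = 8 terms. At the planned rates the expected events are 30 × 0.40 + 30 × 0.20 = 18, or 18 / 8 = 2.25 per term. Separation or non-convergence occurred in about 8–31% of simulated trials. Over rates of 0.15–0.45 the treatment test alone had size about 2–6% by Wald and about 7–13% by likelihood ratio.

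**The case against.** The strongest reply is that the plan already points to the unadjusted comparison. The sample size is built on two independent proportions, and the primary effect is a relative risk, whereas a logistic model yields odds ratios. On that reading the error is about 5% or lower. The pointers are real, and they make the unadjusted test the likelier intention. They are not a rule, though: they leave the logistic model's role open and do not choose between chi-square and Fisher.

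Four stronger readings are tempting, and the documents do not support them:

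- *The error rate does exceed 5%.* Nothing says that significance in any one analysis suffices, and the logistic model is not expressly tied to the primary outcome. The excess is conditional.
- *The chi-square/Fisher choice inflates the error.* Step 2 rules this out. The two can disagree: 12 vs 5 events gives p=0.045 by chi-square and 0.084 by Fisher. But the smallest expected count there is 17 × 30/60 = 8.5, so the usual convention selects chi-square.
- *Switching to Fisher costs material power.* Under the usual convention it does not at the planned rates. The loss at 20% vs 10% lies outside them. Using Fisher throughout would cost about nine points at 40% vs 20% (30% against 39%), but the plan does not say that.
- *Three tests at 5% give 1 − 0.95³ = 14.3%.* That requires independent tests, and these are strongly correlated.

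It is also fair that the size of the excess depends on assumed covariates. That is why a range is given.

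**Conclusion.** The point holds as an omission with a conditional consequence. The decisive primary analysis and the role of the logistic model are both unstated. If either the unadjusted or the adjusted result may be claimed, the two-sided type I error can reach roughly 6–8.5% at event rates of 20–45%, under the assumed tumour types and covariate effects. All of the excess comes from the adjusted model; an open covariate list could add to it, and this was not simulated. If the unadjusted test alone decides, the error stays at about 5% or below.

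The inflation is modest. The point still goes beyond wording, because it concerns the only primary endpoint and one of the competing analyses is unstable at this sample size.

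**What to change.** Before the outcome data are compared by arm, add two sentences to the Statistical Analysis Plan:

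1. The primary outcome is decided by the Mantel–Haenszel chi-square test stratified by centre, without continuity correction and whatever the expected counts, at two-sided 0.05, reported with the Mantel–Haenszel relative risk and its 95% CI.
2. The multivariable logistic model is supportive, and no significance claim rests on it.

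This test fits the randomisation, which is blocked with the aim of balancing the arms across the two centres, and it keeps the relative risk that the plan already promises. In simulation its size stayed near 5% (4.7–5.9%), and it gained up to about 4 points of power when the centres differ. Naming the plain chi-square test would also close the gap, but without that gain.

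The cost is two sentences and no extra data. The downside is that the sponsor gives up the option of relying on the adjusted result.
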